3.2 Eligibility Criteria

Inclusion Criteria

1. Adult patients (≥ 18 years) with hematologic malignancies who have received allogeneic HSCT at the DFCI who are approaching 100-day post-transplant milestone.
2. Ability to speak, read and write English.
3. Access to a telephone.

Exclusion Criteria

1. Cognitive deficits impeding a study participant's ability to provide informed consent or participate adequately in the study procedures assessed via a commonly used 6-item cognitive assessment with the Brief Interview for Mental Status (BIMS).⁵⁷ (Appendix B)
2. Medical conditions precluding interviews.
3. Patients undergoing HSCT for benign hematologic conditions.
4. Patients undergoing outpatient HSCT.
5. Patients with psychiatric or cognitive conditions which the treating clinicians believes prohibits compliance with study procedures.
6. Patients who are unable to consent or are not yet adults (including infants, children, teenagers), pregnant women, or prisoners.

4.0 Study-Wide Number of Subjects*

We propose to recruit 70 patients with hematologic malignancies who have undergone HSCT from one site – DFCI. This is not a multi-site study.

5.0 Study-Wide Recruitment Methods

5.1 Recruitment and Enrollment Procedures:

Prior to study start, the PI will present at the DFCI HSCT protocol meeting to inform the HSCT clinicians about the study and to alert them to the screening, recruitment, and enrollment procedures. The CRC will screen the DFCI HSCT clinic database to recruit, screen, and identify potentially eligible patients. The CRC will then email the transplant oncology clinician to notify them that the patient is potentially eligible for study participation and to inquire about any concerns regarding their study participation (Appendix C). If the treating transplant clinician has any concerns regarding a patient's study participation, then the CRC will document the reason and not approach that individual. If there is no concern regarding study participation, the CRC will approach patients for study participation as they approach their 70-80-day post transplant recovery milestone over the phone or in clinic and ask if they are interested in participating (Appendix D). Patients will only be contacted twice over the phone and will be provided with a call back number to either opt-in or opt-out of the study. Interested participants will be screened with the BIMS and provided (in-person at clinic, mailed or e-mailed) an information sheet of the study to review prior to their completing consent procedures. Patients will have the option of enrolling in the study in-person at the patient's scheduled clinic visit or over the telephone with a

PROTOCOL TITLE: Randomized Trial of a Positive Psychology Intervention for Patients with Hematologic Malignancies Undergoing Hematopoietic Stem Cell Transplantation

verbal consent (Appendix E) seven days after receiving the study information sheet. Consented participants will then receive an *Actigraph GT3X+* and MEMS Cap for baseline (Day 85-90 post-HSCT) physical activity and medication adherence assessment, respectively. Additionally, consented participants will complete baseline assessments around Day 85-90 post-HSCT.

Participants who provide verbal consent will be asked to sign HIPAA Authorization to review their medical records for the purposes of research. HIPAA authorization maybe provided at a clinic visit or remotely over e-mail or via mail in the setting of the COVID-19 stipulations. Participants who complete written informed consents will sign a HIPAA authorization as part of the written informed consent.

Participants will be registered with the Clinical Trials Management System after they have consented, provided baseline *Actigraph GT3X+* data, and completed baseline assessments. If participants provide consent but do not complete baseline Actigraph data collection and assessments, they will not count towards accrual numbers. Participants who withdraw from the study or die during the study period will not be replaced and they will count towards accrual numbers.

DF/HCC institutions will register eligible participants in the Clinical Trials Management System (CTMS) Oncore as required by DF/HCC SOP REGIST-101. Registration must occur after the initiation of protocol-specific procedures or assessments.

For registration of participants from the DF/HCC institutions, study staff will complete the DF/HCC protocol-specific eligibility checklist. Study staff will confirm that the participant meets all inclusion criteria as described in this protocol. Study staff will then register study participants through OnCore. Study staff will follow DF/HCC Standard Operating Procedure for Human Subject Research Titled *Subject Protocol Registration* (SOP #: REGIST-101) and register the participant on the protocol.

Once the patient has been registered, a member from the MGH Cardiac Psychiatry Research Program (CPRP) team or the Cancer Outcomes Research and Education Program (CoRE) (independent from the study staff) will perform randomization procedures using a computer-generated randomization schema, stratified by GVHD status.

6.0 Multi-Site Research

Not Applicable. This research is located at one site – the DFCI main campus

7.0 Study Timelines*: Table 1 depicts the expected study timeline.

Time Point	Table 1: Study Procedure
Months 0-2	Finalize protocol development and submit to Institutional Review Board for approval
Months 3-4	Staff Training ❖ Hire CRC and train them in study procedures, recruitment, and data collection.
Months 5-29	Randomized Controlled Trial: ❖ Enroll and randomly assign 70 patients (35 per study group) to receive either the PATH intervention vs. usual care control.
Months 30-35	Data Collection: ❖ Complete longitudinal data collection with a minimum of 1 year follow-up on all study participants.
Months 36-40	Data Analysis: ❖ Complete data analysis and submit primary manuscripts. ❖ Prepare and submit grant proposal for large scale multi-site randomized controlled efficacy study.

PROTOCOL TITLE: Randomized Trial of a Positive Psychology Intervention for Patients with Hematologic Malignancies Undergoing Hematopoietic Stem Cell Transplantation

Each participant will be enrolled for approximately one year to collect patient-reported outcomes. We estimate that we will complete the primary manuscripts in months 57-60 from the study start period.

8.0 Study Endpoints*

Primary Endpoint:

- Establish feasibility and acceptability of the PATH intervention in the intervention group.

Secondary Endpoints:

- Compare patients' QOL (FACT-BMT) scores longitudinally between the study groups
- Compare patients' positive psychological wellbeing factors [e.g., optimism (LOT-R) and positive affect (PANAS)] between the study groups
- Compare patients' symptoms of anxiety and depression (HADS) between the study groups
- Compare patients' post-traumatic stress symptoms (PCL-C) between the study groups
- Compare patients' fatigue (PROMIS-fatigue) scores between the study groups
- Compare patients' physical activity (Actigraph GT3X+ data) and physical functioning (PROMIS-PF-20) between the study groups
- Compare patients' medication adherence (MEMS Cap data, SSEQ, MARS-5) between the study groups
- There are currently no anticipated primary or secondary safety endpoints.

Exploratory Endpoints:

- Compare patients' coping (Brief Cope) between the study groups
- Assess whether group differences in patient reported QOL are mediated by improved mood (mediator: HADS) or coping (mediator: Brief Cope)

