- 1.1.6. **PTSD symptoms:** We will use the Post-Traumatic Stress Disorder Checklist (PCL) to assess symptoms of post-traumatic stress in patients. The PCL is a 17 item self-reported measure that evaluates symptoms of post-traumatic stress disorder according to the criteria of the Diagnostic and Statistical Manual of Mental Disorders-IV.⁶⁵ (Appendix L)
- 1.1.7. **Optimism:** We will use the 10-item Life Orientation Test-Revised (LOT-R) to measure dispositional (trait) optimism. Higher scores indicate greater optimism.⁶⁶ (Appendix M)
- 1.1.8. **Positive Affect:** We will use the 10-item Positive and Negative Affect Schedule (PANAS) to measure positive affect; higher scores indicate greater positive and negative affect.⁶⁷ (Appendix N)
- 1.1.9. **Social Support:** We will assess social support using the 26-item Social Support Effectiveness Questionnaire (SSEQ), a validated instrument used in oncological population to assess patients' perception of social support.^{68, 69} (Appendix O)
- 1.1.10. **Coping strategies:** We will use the Brief Cope, a 28-item questionnaire that assess 14 methods of coping (e.g., self-distraction, humor, denial) using a 4-point Likert scale.⁷⁰ (Appendix P)
- 1.1.11. **Satisfaction:** We will use the 5-item Satisfaction with Life Scale (SWLS) to measure satisfaction with life; higher scores indicate greater satisfaction with life.⁷¹ [Appendix Q]

PROTOCOL TITLE: Randomized Trial of a Positive Psychology Intervention for Patients with Hematologic Malignancies Undergoing Hematopoietic Stem Cell Transplantation

1.1.12. **Gratitude:** We will use the 6-item Gratitude Questionnaire to measure dispositional gratitude; higher scores indicate greater proneness to experience gratitude in daily life.⁷² [Appendix R]

1.1.13. **Purpose and Flourishing:** We will use the 8-item Flourishing Scale to assesses a person's self-perceived success in critical areas such as engagement, relationships, self-esteem, meaning & purpose, and optimism; higher scores indicate many psychological resources and strengths.⁷³ [Appendix S]

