1.1.14. **Health Behaviors:** Physical activity and medication adherence will be the target behavioral outcome measures. We will use the well-validated Actigraph GT3X+ accelerometer,⁷⁴ at baseline, Week 9, and Week 18, for 7 days of wear; minimum acceptable use is 4+ days with 10+ hours of recorded data as in prior guidelines⁷⁵⁻⁷⁷ to measure minutes/day of light activity (100-1951 counts/min⁷⁸) as our primary activity measure, along with sedentary leisure time (SLT),^{74, 79} given their links to health outcomes. Medication (specifically immunosuppressant, tacrolimus or sirolimus) adherence will be measured via the widely used electronic pill monitoring system, MEMS Caps,⁸⁰ to electronically monitor immunosuppressant adherence over the duration of the study. From the EHR and confirmed by patients, we will determine immunosuppressant medication and dosing, and we will calculate changes in adherence over time (% of medication correctly taken, by week and month), based on MEMS data. Additionally, we will assess self-reported adherence to Tacrolimus (an immunosuppressant medication which all allogeneic HSCT patients must take) with the Medication Adherence Scale-5 (MARS-5).^{81, 82} (Appendix T)

9.5 Data from the Electronic Health Record:

Study staff will collect clinical, disease, and transplant characteristics at baseline including: ECOG Performance Status at the time of HSCT, clinical comorbidities as measured by the HCT-Comorbidity Index,⁸³ underlying diagnosis, date of diagnosis, disease status at the time of HSCT, disease risk based on the Disease Risk Index,⁸⁴ conditioning regimen, donor type, donor source, date of HSCT, and hospital length-of-stay. We will also collect data on the incidence and severity of acute and chronic GVHD and the incidence of relapse at one year post-HSCT as these outcomes are associated with QOL.

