We will compare between-group differences in change over time in all patient-reported outcome measures (i.e., psychological, functional, and QOL outcomes) at the 9 and 18-week time points using random effects regression models with a random intercept for each patient. Longitudinal analyses will include all time points. The model will include a categorical effect of time (baseline, week 9 and week 18), a group effect and a time by group interaction. The time by group interaction will estimate the difference in the change from baseline to each time point, and these regression coefficients will be the focus of the analysis.

Given that this pilot is not powered to detect statistically significant group differences, we will examine difference in the change with time and sample variance components on the secondary outcomes. Effect sizes (Cohen's d) will be calculated for changes in outcomes from baseline to 9 and 18 weeks, where 0.3 indicates a small effect, 0.5 a medium effect, and 0.8 a large effect.⁸⁸ Effect sizes will be used in a power analysis to estimate the necessary sample size to conduct a full-scale efficacy trial with power >80%. We will also verify the needed sample size based on ability to detect a clinically meaningful difference and references to existing literature.⁸⁹

Finally, we will explore (1) possible mediators of the intervention (e.g., coping strategies) by examining the bootstrapped confidence intervals of the indirect effects and (2) possible moderators (e.g., social support) of intervention effects by probing interactions between the moderator and group assignment that reach or approach significance ($p<0.15$) when predicting patient-reported outcomes.

PROTOCOL TITLE: Randomized Trial of a Positive Psychology Intervention for Patients with Hematologic Malignancies Undergoing Hematopoietic Stem Cell Transplantation

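### Section 8.0 lists the SSEQ, a social-support questionnaire, among the measures of the medication-adherence endpoint; it should come out of that bullet and be given its own role

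*Combined protocol and SAP*

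**What the plan says.** Section 8.0 (Study Endpoints) includes among the secondary endpoints a comparison of "medication adherence (MEMS Cap data, SSEQ, MARS-5) between the study groups". Three instruments are therefore attached to adherence.

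Section 9.4 (Selection of Instruments) treats them differently. Under its Social Support item it describes the SSEQ as "a validated instrument used in oncological population to assess patients' perception of social support". Under Health Behaviors it says that immunosuppressant "adherence will be measured via the widely used electronic pill monitoring system, MEMS Caps", and it adds the MARS-5 as the self-report measure. The SSEQ is not mentioned there.

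Table 4 in section 9.6 schedules the SSEQ at baseline, week 9 and week 18 without saying what it is for. Section 10.1, at the end of Aim 2, proposes to explore "possible moderators (e.g., social support) of intervention effects by probing interactions between the moderator and group assignment". Section 10.1, Aim 3, compares change in medication adherence between groups with a random-intercept model and names no adherence instrument.

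**The concern.** The endpoint list is where an analyst looks first for what to compare, and here it assigns an instrument to a construct that the instrument does not measure by the protocol's own definition. Because Aim 3 refers only to adherence in general, the analyst must take the instruments either from section 8.0 (three) or from section 9.4 (two).

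If section 8.0 is followed as written, a between-arm difference in perceived social support could be reported as an effect on adherence. Nothing in the data would expose the mistake: the SSEQ is collected at every assessment, so the comparison can be run without difficulty.

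**Working it through.** No figure in the plan is at issue, so the check sets the relevant places side by side.

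| Place | What it says about the SSEQ | What it says about adherence |
|---|---|---|
| 8.0, secondary endpoints | Listed as an adherence measure | MEMS Cap data, SSEQ, MARS-5 |
| 9.4, Social Support | 26 items, perceived social support | Not mentioned |
| 9.4, Health Behaviors | Not mentioned | MEMS Caps and MARS-5 |
| 9.6, Table 4 | Baseline, week 9, week 18; no construct given | MARS-5 at all three times; MEMS Cap from baseline through week 9 |
| 10.1, Aim 2 | Not named; social support is an example of a moderator | Not mentioned |
| 10.1, Aim 3 | Not named | Outcome named, instrument not |

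1. **Is there a second meaning of the abbreviation?** No. Section 9.4 gives the only expansion, and it is a social-support scale.

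2. **Does anything besides section 8.0 tie the SSEQ to adherence?** No. The abbreviation appears in section 8.0, in section 9.4 and in Table 4. Only section 8.0 makes the link.

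3. **Does the analysis section resolve it?** No. Aim 3 gives a model and a two-sided 0.05 criterion. It gives no list of adherence instruments, no ranking among them and no rule for combining them.

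4. **How much of the endpoint is affected?** Of the three instruments in the bullet, two measure adherence by the protocol's definitions and one does not: 3 − 2 = 1. On Table 4's schedule the MEMS Cap stops at week 9, and section 9.7 has it returned then. On that schedule the bullet's instruments at week 18 are the MARS-5 and the SSEQ, one of each kind. Section 9.4 speaks instead of MEMS monitoring for the duration of the study, so the week 18 count depends on which of these holds. These are counts of instruments, not estimates of bias.

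5. **Does its classification matter for testing?** Only for the SSEQ itself. As an adherence measure it would be tested under Aim 3 at two-sided 0.05. If it is instead treated as a patient-reported outcome under Aim 2, the stated rule is alpha 0.2 with a Bonferroni correction. The number of tests in that correction is not given, so no per-test threshold can be calculated. The criterion for MEMS and the MARS-5 is the same either way.

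**The case against.** The strongest reply is that this is a misplaced abbreviation and that the protocol already contains the right answer. Section 9.4 defines adherence in operational terms: percentage of medication correctly taken from MEMS data, plus self-report on the MARS-5. It also gives the SSEQ its own item under social support. No rule exists for scoring the SSEQ as adherence. A careful analyst would follow section 9.4, and in a pilot that section 10.2 says is not designed to detect group differences definitively, little would turn on it.

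Most of that stands. It limits the consequence but does not remove the error, because the wrong entry is in the operative endpoint list and Aim 3 does not override it.

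A reader might infer four stronger things that the documents do not support:

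- *The whole adherence endpoint is invalid.* MEMS and the MARS-5 remain valid measures of it.
- *The extra instrument inflates error in an adherence test family.* No such family is defined, and Aim 3 states no multiplicity adjustment that an added test would disturb.
- *Using one scale as both moderator and outcome is itself a flaw.* A baseline score can serve as a moderator while later scores are compared between arms.
- *The SSEQ was meant to be a moderator only.* Section 10.1 offers social support as an example, and collection at all three time points fits a longitudinal outcome equally well.

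**Conclusion.** The inconsistency is real and internal to the document: section 8.0 assigns the SSEQ to medication adherence, and section 9.4 assigns it to social support and leaves it out of the adherence measures. It affects one instrument of three in one secondary endpoint, and it causes harm only if section 8.0 is applied literally. The primary endpoint, the sample size and the other two adherence measures are untouched. It should be corrected as a matter of consistency, and no claim of bias or error inflation should be attached to it.

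The conclusion assumes that section 9.4's definition of the SSEQ is the intended one, which is the only reading the document offers. A reader might also suppose that the registry carries the same mistake. Section 11.0 commits the trial to registration and results reporting, but the registered outcome wording is not in the document, so this can only be checked, not asserted.

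**What to change.** 1. In section 8.0, delete SSEQ from the medication-adherence bullet, leaving MEMS Cap data and MARS-5 to match section 9.4.
2. Give the SSEQ its own entry as a social-support measure. The sponsor may make it a separate secondary or exploratory comparison, a moderator under section 10.1, or both. Without such an entry it would have no stated place in section 8.0 once removed from the adherence bullet.
3. Where it is used as a moderator, say in section 10.1 that the baseline score is used, since later scores could themselves be affected by the intervention.
4. In section 10.1, Aim 3, name MEMS Cap data and the MARS-5 as the adherence measures, so that the analysis text no longer depends on the endpoint list.
5. Check the registry entry and correct it if it repeats the error.

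The cost is one deletion and two or three short sentences. Data collection, the visit schedule and the sample size do not change.

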9.0 Procedures Involved*

9.1 Study Design

We propose a single center randomized trial of a positive psychology intervention (PATH) versus usual care in 70 patients with hematologic malignancies undergoing HSCT. Participants will be randomized equally to the two arms using randomized permuted blocks of sizes two and four, with randomization stratified by presence/absence of GVHD. As allogeneic transplant recipients with GVHD have significantly different courses of recovery, QOL, and function post-transplant, we will stratify by GVHD status to ensure adequate and balanced representation between the two study groups.

PROTOCOL TITLE: Randomized Trial of a Positive Psychology Intervention for Patients with Hematologic Malignancies Undergoing Hematopoietic Stem Cell Transplantation

The goals of this study are to assess the feasibility, acceptability and preliminary efficacy of this novel 9-session, weekly PP-based intervention for HSCT patients.

Patients will be contacted via telephone or in person at a routine clinic visit close to their routine 70-80-day post-transplant visit for eligibility determination. Interested patients will be screened based on the inclusion/exclusion criteria and provided a study information sheet via mail, e-mail or in-person at a routine clinic visit. Consent procedures would be completed in-person at a routine clinic visit or verbally over the phone approximately seven days after study information is provided.

Upon consent to participate in the study, participants will be given an electronic pill bottle (MEMS Cap) [to be used from the time of baseline assessment completion through the entire duration of the intervention], and an accelerometer to be worn for 7 days prior to the initiation of the intervention. Between the 85-95-day point, all participants will also complete baseline questionnaires either in person, over phone or via a REDCap survey link to participants. Additionally, participants randomized to the intervention group will be given an intervention manual with 9 weekly PP exercises.

Participants randomized to the intervention group will be asked to complete 9 weekly PP exercises and to speak with the study interventionist, weekly. Immediately after the completion of each exercise, participants will rate the ease of exercise completion, overall utility of the exercise, and their current levels of positive affect. Prior to the last week of the intervention, all participants (regardless of whether they are in the intervention group or usual care group) will be mailed (or given in person at a routine follow-up clinic visit) an accelerometer to be worn for 7 days prior to the follow-up survey. After the Week 9 intervention phone session, all participants (regardless of whether they are in the intervention group or usual care group) will repeat self-assessment questionnaires completed at baseline either over the phone, in-person at a routine clinic visit or via a REDCap survey link emailed to participants. Additionally, participants randomized to the intervention group will be asked to complete a recorded exit interview (Appendix F) over the phone. At study completion, we will inquire about participants' potential interest in being contacted about our future studies. We will adhere to any and all participant requests regarding contact. Participants will also return the accelerometer and MEMS Caps at the end of the study via mail or in person during a routine follow-up clinic visit. All participants will receive a \$50 check after the 9-week follow-up assessments. Participants who complete the 18-week follow-up assessments will receive an additional \$50 check.

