any participants refuse or are unable to complete the questionnaires on the computer, they will be permitted to use hard-copy paper versions of the questionnaires. Participants will also be provided the option to complete questionnaires over the phone. The CRC will contact participants (in person or via telephone) daily for two days to remind them to complete and return the surveys. If study participants fail to complete the surveys within seven days of the expected time point, we will report the data as missing and document the reason for incompleteness. Table 4 details the schedule for administering the self-report measures. At enrollment all participants will be mailed the *Actigraph GT3X+* (together with instructions (Appendix V) on how to use the *Actigraph*) for 7 days of wear; minimum acceptable use is 4+ days with 10+ hours of recorded data around day 85-95 post-transplant and prior to the intervention initiation around day 100 post-transplant. After baseline physical activity data collection, participants will mail back the *Actigraph* in prepaid envelopes we will provide. In addition to the *Actigraph*, participants will also be mailed the MEMS Cap (together with the instructions (Appendix W) on how to use the MEMS Cap) for medication (immunosuppressant) adherence assessment over the entire duration of the intervention starting at the time of baseline surveys around day 85-95 post-transplant. All participants will complete baseline assessments approximately 85-95 day post-transplant. All participants will then complete follow-up assessments at Week-9 (with a 1 week window) and at Week-18 (+/- 1 week window) of intervention initiation.

Table 4: Administration of Self-Report Measures

Participant	Baseline	Week-9 (+ 1 week window)	Week-18 (+/- 1 week window)
Patient Measures:			
Demographics	X		
FACT-BMT	X	X	X
PROMIS-Fatigue 8a	X	X	X
PROMIS-PF-20	X	X	X
HADS	X	X	X
PCL (PTSD)	X	X	X
LOT-R	X	X	X
PANAS	X	X	X
GQ-6	X	X	X
SWLS	X	X	X
Flourishing Scale	X	X	X
Brief Cope	X	X	X
MARS-5	X	X	X
SSEQ	X	X	X
Accelerometer	X	X	
MEMS-Cap		Longitudinal from baseline through week 9	

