Specific Aim 3 (Effects on Health Behaviors): To examine the impact of the PATH intervention on behavioral outcomes (e.g., medication adherence, physical activity) compared to those in the usual care condition: We will initially compare physical activity (# of steps/day) at 9- and 18-weeks between the intervention and control groups using a Wilcoxon rank sum test, given that the distribution of the number of steps will likely be skewed. We will also use random effects regression models with a random intercept for each participant to compare between-group differences in change over time in physical activity and medication adherence. All statistical tests will be two tailed, with $p < 0.05$ considered significant.

Missing Data: We will also use the intention-to-treat principle with all randomized participants and conducting sensitivity analyses to explore various assumptions about missing data. If source of the missing data appear to be missing at random, the linear mixed effects models described above provide an unbiased estimate of the regression coefficients. However, if we find that participants do not complete the study because of disease worsening, suggesting missing data are not random, we will employ pattern mixture modeling or joint modeling approaches⁹⁰ to handle incomplete data, and perform sensitivity analysis⁹¹ to assess the impact of missing data. In addition to the intention-to-treat analysis, we will also estimate the group differences in the completers to estimate the per protocol group difference.

10.2. Sample Size Calculation & Power Analysis:

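### For the MEMS measure, the documents guarantee no adherence data before randomisation, although the cap is already handed out at consent

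*Combined protocol and SAP*

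**What the plan says.** **Start of recording.** Section 9.1 gives participants the cap at consent, but it is "to be used from the time of baseline assessment completion through the entire duration of the intervention". Section 9.6 describes "adherence assessment over the entire duration of the intervention starting at the time of baseline surveys around day 85-95 post-transplant", and the MEMS row of Table 4 reads "Longitudinal from baseline through week 9". Section 5.1 differs: after consent, participants receive the accelerometer and "MEMS Cap for baseline (Day 85-90 post-HSCT) physical activity and medication adherence assessment". No section defines a MEMS baseline window.

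**Time of randomisation.** In Section 5.1, registration waits for consent, baseline accelerometer data and the baseline assessments. It does not name cap data. Randomisation comes next: "Once the patient has been registered, a member from the MGH Cardiac Psychiatry Research Program (CPRP) team" (or an independent member of a second group) carries it out. Section 21.0 also randomises after registration. Section 9.7 has consented participants randomised straight away, and describes the distribution of devices and the baseline surveys after that.

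**Analysis.** Section 9.4 (Health Behaviors) derives the percentage of immunosuppressant taken correctly, by week and month, and its change over time. For Aim 3, Section 10.1 uses random-intercept models to "compare between-group differences in change over time in physical activity and medication adherence". MEMS is one of the adherence measures among the secondary endpoints in Section 8.0. MARS-5, the self-report measure, is collected at baseline, Week 9 and Week 18 (Table 4).

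**The concern.** An analysis of change over time by arm is easiest to interpret when it starts from a period that allocation cannot have influenced. The accelerometer is set up that way under Section 5.1: 7 days of wear, with baseline data required before registration. The cap is handed out at about the same time, but Sections 9.1 and 9.6 leave it unused until the baseline surveys.

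Two things are at stake. First, if the earliest MEMS days serve as the reference and fall after allocation, adherence may already differ by arm. Measuring change from them could then remove part of an effect or add a spurious one. Second, a pre-randomisation measure of the same quantity can be used as a covariate to reduce residual variance, which is valuable with about 30 completers per arm. A pre-randomisation period that was not recorded cannot be recovered later.

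**Working it through.** **Step 1: order of events.** The sections give these combinations:

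| Sections combined | MEMS starts | Randomisation | Pre-randomisation MEMS days |
|---|---|---|---|
| 9.1 with 5.1 | when baseline assessments are complete | after registration | 0 guaranteed; some possible if accelerometer data arrive after the surveys |
| 9.6 and Table 4 with 5.1 | at the baseline surveys | after registration | 0 guaranteed; some possible, as above |
| 9.1 or 9.6 with 9.7 | as above | directly after consent | none |
| 5.1 alone | for a baseline assessment at day 85-90; start not stated | after registration | intended, but no window defined |

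**Step 2: day arithmetic on the stated windows.** Inputs: first approach at day 70-80 (Section 5.1); consent about 7 days after study information (Section 9.1), taking the information to be given at first approach; baseline at day 85-95 (Sections 9.1, 9.6); intervention start at about day 100 (Section 9.2).

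- Consent: 70 + 7 = day 77, to 80 + 7 = day 87.
- Cap in hand before the surveys: shortest 85 − 87 = −2, so 0 days; longest 95 − 77 = 18 days. The range is about 0-18 days. The 7-day accelerometer wear suggests about 7 as the nominal figure.
- Surveys to intervention start: 100 − 95 = 5 days, to 100 − 85 = 15 days.

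Up to about 18 days of possession therefore go unrecorded under Sections 9.1 and 9.6. The 5-15 days before the intervention are recorded, but the documents do not fix how many of them precede randomisation.

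**Step 3: the plan's detectable effect.** Section 10.2 states that d = .74 is needed for 80% power at p < .05 with 30 completers per group, and includes behavioural outcomes in that statement. A two-sample t-test with n = 30 per group, two-sided alpha 0.05 and d = 0.74 has 80.5% power (normal approximation 81.8%). The d that gives exactly 80% is 0.736. The stated figure reproduces and is not in dispute.

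**Step 4: what baseline adjustment could add.** The documents give no correlation r between baseline and follow-up MEMS adherence, so r is an assumption, shown as a range. For a single follow-up measure adjusted for baseline, the variance is multiplied by 1 − r², and the detectable d is 0.736 × √(1 − r²). For a raw change score the multiplier is 2(1 − r).

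| Assumed r | 1 − r² | Detectable d, baseline as covariate | 2(1 − r) | Detectable d, raw change score |
|---|---|---|---|---|
| none used | 1 | 0.74 | – | – |
| 0.3 | 0.91 | 0.70 | 1.40 | 0.87 |
| 0.5 | 0.75 | 0.64 | 1.00 | 0.74 |
| 0.7 | 0.51 | 0.53 | 0.60 | 0.57 |

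The covariate form does better than the raw change score at each of these values, which is why the fix uses baseline adherence as a covariate.

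**The case against.** The strongest reply is that nothing in the plan becomes invalid. Section 10.1 speaks of change over time for Aim 3. The model that contrasts baseline with each later time point is specified there for the Aim 2 patient-reported outcomes. A weekly adherence trajectory compared by randomised arm needs no pre-randomisation baseline. MEMS is also one secondary measure in a feasibility pilot that Section 10.2 says is not designed to detect group differences definitively. All of this stands, and it limits the point to a lost reference period and lost precision.

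A reader might infer more, but the documents do not support these stronger readings:

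- *Adherence has no baseline at all.* MARS-5 has one, and under Section 5.1 it precedes randomisation. It is self-report, however, and does not replace electronic monitoring.
- *All MEMS data follow randomisation, with participants knowing their arm.* That follows under Section 9.7. Under Section 5.1, registration also waits for the accelerometer data. Devices are mailed back (Section 9.6) and insufficient wear is repeated (Section 9.7), so a cap started at the surveys may record some days before randomisation. The number is unspecified.
- *The protocol has settled on omitting a MEMS baseline.* Section 5.1 asks for one, so the sections conflict.

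The precision figures are also open to challenge. They rest on an assumed r and a single follow-up measure, not on the repeated-measures model of Section 10.1, and at r = 0.3 the gain is small.

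Finally, if Section 9.7 governs the order, starting the cap at consent would yield about zero pre-randomisation days. The fix works only if the order is settled first.

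**Conclusion.** The point holds for MEMS only. As written, the documents guarantee 0 days of pre-randomisation MEMS adherence, while Section 5.1 calls for a baseline adherence assessment and Sections 9.4 and 10.1 analyse change over time. The comparison of MEMS adherence between arms remains valid and the primary feasibility endpoint is unaffected. What is lost is a clean reference period and the option of baseline adjustment. As an illustration for a single follow-up measure, adjustment would lower the detectable d from 0.74 to about 0.70, 0.64 or 0.53 at assumed correlations of 0.3, 0.5 or 0.7. The day counts assume the nominal windows are kept and that study information is given at first approach. The change is worth making because the cap is already in the participant's hands.

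**What to change.** 1. Reconcile Sections 5.1, 9.1, 9.6 (with Table 4) and 9.7 so that randomisation follows completion of baseline in every place and the start of MEMS recording is stated once.
2. Start recording when the cap is handed out at consent, alongside the 7-day accelerometer wear.
3. Define baseline adherence as the percentage taken correctly in the days before randomisation. On the stated windows this gives about 0-18 days before the surveys, nominally about 7. State how participants with few or no such days are handled.
4. Include baseline adherence as a covariate in the Week 1-9 MEMS adherence model in Section 10.1.

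If this is not done, describe the MEMS analysis as a post-randomisation comparison of adherence between arms, and do not present the first MEMS days as a baseline.

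The cost is revised participant instructions, the text changes above and a slightly longer recording period per participant. No new device or visit is needed.
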